5.5.1 CASE HISTORY

Demographics:

Demographic information from the participant will be obtained, including age and sex.

Medical History:

At screening, information will be obtained from participants about the current medication, allergies, and any medical conditions. At visits 1B-R and Visit 2 participants will be asked about changes in their medication or health.

5.5.2 SUBJECTIVE RATINGS

Subjective ratings:

After a successful insertion/ removal training at Visit 1 or Visit 1B-R, participants will complete subjective post-handling training ratings (0-100 scale, where 100 means better handling) for **each eye individually**. Separate ratings and comments for:

- Ease of insertion
- o Ease of removal

A Visit 2, participants will be provided with subjective rating questionnaires for wear experience with both CLs (0-100 scale, where 100 means better performance; integer steps, ratings for **each eye individually** for a typical day in the last week);

- Comfort (at insertion and just before removal)
- Handling (insertion & removal)
- General" handling questions, to be evaluated at Visit 1 (based on initial training) & at Visit
 2 (after 1 week of wear), including

- o "Ease of opening package",
- o "Ease of removing lens from package",
- o "Ease of telling whether lens is inside/out"
- "Stability on finger"
- Preference ratings between study lenses: (Likert scale; including strongly prefer L1, slightly prefer L1, no preference, slightly prefer L2, strongly prefer L2)
 - Comfort
 - Handling for insertion
 - Handling for removal
 - o Overall
 - Willingness to purchase

5.5.3 VISUAL ACUITY

Visual acuity will be measured using high contrast computer-generated acuity charts.

Participants will be asked to read letters that progressively decrease in size on a computer screen located at a distance of 6 meters. Measurements will be taken during the subjective refraction, with study lenses and habitual spectacles.

5.5.4 AUTOREFRACTION

Participants will be asked to focus on a target while seated at an instrument that measures their approximate spectacle prescription and corneal shape.

5.5.5 SUBJECTIVE REFRACTION

Participants will be asked to read a letter chart from a distance through lenses placed in front of their eyes. They will also be asked to compare clarity of your vision between different lenses placed in front of your eyes. This procedure aids to determine their spectacle and/or contact lens prescription.

5.5.6 LENS PERFORMANCE

Contact lens fit:

Overall Lens Fit acceptance will be assessed to ensure acceptable lens fit with the study lenses using a 0-4 scale (0.5 step, 0= perfect lens fit), in addition, Lens Tightness (0-100, 1 step – 100 = no movement) and Lens Centration (0-3, 1 step, 0= optimally centred) will be collected.

Contact lens wettability:

Contact lens wettability will be graded using e.g. 32x magnification, on a 0-4 scale, 0 = excellent wettability, 0= no deposits (0.25step).

5.5.7 SLIT LAMP BIOMICROSCOPY

The participant will be seated behind a slit lamp and the following will be assessed:

Cornea:

Any current or past corneal observations (such as infiltrates, old scars, etc) will be documented at each visit.

Corneal and conjunctival staining:

A sodium fluorescein strip, wetted with a few drops of saline, will be applied to the superior bulbar conjunctiva of both eyes. Staining will be graded using the Efron grading scale (0 to 4, 0 = normal) in 0.1 scale increments, while viewing with cobalt blue light through a Wratten no. 12 barrier filter.

Bulbar and limbal hyperemia:

Ocular redness will be assessed for the bulbar and limbal conjunctiva using the EFRON grading scale (0 to 4, 0 = normal; 0.1 increments). Redness will also objectively be assessed using an imaging technique provided by the Oculus K5M.

Palpebral conjunctival hyperemia and roughness:

The redness and roughness of the upper and lower eyelids (tarsal plate zone 2) will be assessed using the Efron grading scale (0 to 4, 0 = normal/ uniform satin appearance).

6 MONITORING PROTOCOL ADHERENCE

All personnel involved in this study will be listed on a delegation log and their training will be documented. Consent documentation will be reviewed by personnel not involved in the consent process. Visit windows will be reviewed when determining the analysis cohort. All adverse events and protocol deviations will be reviewed by the Lead Investigator. Serious adverse events and major protocol deviations will be reviewed by the Principal Investigator.

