2 OBJECTIVES

The objectives of the study are:

- Subjective ratings of lens handling for insertion and removal as determined during the handling training component of Visit 1 (Or Visit 1B-R) (i.e. the first exposure of the participants to handling contact lenses; 0 to 100 scale) for each lens.
- Additional "general" handling questions to be evaluated may include "Ease of opening package", "Ease of removing lens from package", "Ease of telling whether lens is inside/out" or "Stability on finger". These questions will be evaluated after training session (Visit 1 and Visit 1B-R)) and after 1 week of wear (Visit 2), using 0 100 ratings.

Primary Endpoint:

 Subjective ratings of lens handling for insertion and removal as determined during the handling training component during Visit 1 (and Visit 1B-R) (i.e. the first exposure of the participants to handling contact lenses; 0 to 100 scale)

Other Endpoints:

- Subjective ratings of comfort and handling after 1 week of wear, considering a "typical day" (0 to 100 scale)
- Lens preference after 1 week of wear for Handling for Insertion & Handling for Removal (Likert scale; including strongly prefer Lens1, slightly prefer Lens1, no preference, slightly prefer Lens2, strongly prefer Lens2)
- Subjective ratings (0 100 scale) of "general" handling questions, to be evaluated at Visit
 1 and Visit 1B-R (based on initial training) & at Visit 2 (after 1 week of wear), including

"Ease of opening package", "Ease of removing lens from package", "Ease of telling whether lens is inside/out" and "Stability on finger".

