5.2 STUDY POPULATION

5.2.1 SAMPLE SIZE CALCULATION

The sample size required for a 2-tailed matched paired t-test to detect a change of 5 points in subjective ratings of handling for insertion and removal, with α =0.05, power = 0.90, and an effect size of 0.60 is 32 to complete the study and be eligible for data analysis (a sample size of 32 participants excluding possible dropouts and screen failures).

Up to 60 participants may be randomized to and dispensed with 1-Day ACUVUE Moist and Precision1 DD CLs, to account for potential drop-out in neophytes e.g. due to adaptation/handling issues.

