5.2.2 NUMBER OF PARTICIPANTS

Up to 60 participants may be recruited using CORE records and advertising approved by the UW Office of Research Ethics. Up to 60 participants may be randomized to and dispensed with study products, with a target of number of 32 participants completing the study. Informed consent will be obtained for all participants prior to their enrolment in the study (Appendix 1).

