- Confirmation of eligibility capable of insertion/removal of CLs; participants who are NOT able to remove/insert the study lenses 3x will be offered to attend a re-training session (Visit 1B-R), at which the training will be repeated. Only those participants able to insert/remove lenses at Visit 1 (or Visit 1B-R) will continue in the study.
- **PRIMARY OUTCOME VARIABLE** (only if participants have passed the CL handling training): subjective post-handling training ratings (0-100 scale, where 100 means better handling) for **each eye individually**. Separate ratings and comments for:
 - Ease of insertion
 - Ease of removal
 - General handling questions (not primary outcome variable)
- LogMAR HIHC VA for OD, OS and OU (If returning for Re-training: habitual spectacles, if lenses are dispensed today: study CL)
- Lens wear instructions (only after a successful training)
- Booking of Follow-up visit(only after a successful training)
- Lens dispense (equal number of pairs as there are days until next visit day, plus 3 spare
 pairs in case of handling issues); each px will keep the same lens type (L1 or L2) for
 each eye as randomized to for handling training (e.g. if Precision1 was used on OD for
 training, Precision1 will be worn on OD for 1 week of wear) (only after a successful
 training)

Visit 1B-R: Handling Re-Training (optional) (1hr)

Those participants who did not pass the handling training at Visit 1 will repeat this
training, following the same randomization schedule as determined during Visit 1. If a
participant passes the handling training (i.e. they successfully inserted and removed
each lens 3x), the remaining steps from Visit 1, starting at "PRIMARY OUTCOME
VARIABLE", will be completed.

- **PRIMARY OUTCOME VARIABLE** (only if participants have passed the CL handling training): subjective post-handling training ratings (0-100 scale, where 100 means better handling) for **each eye individually**. Separate ratings and comments for:
 - Ease of insertion
 - Ease of removal
 - General handling questions (not primary outcome variable)
- LogMAR HIHC VA for OD, OS and OU (If returning for Re-training: habitual spectacles, if lenses are dispensed today: study CL)
- Lens wear instructions (only after a successful training)
- Booking of Follow-up visit(only after a successful training)

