- Lens dispense (equal number of pairs as there are days until next visit day, plus 3 spare pairs in case of handling issues); each px will keep the same lens type (L1 or L2) for each eye as randomized to for handling training (e.g. if Precision1 was used on OD for training, Precision1 will be worn on OD for 1 week of wear) (only after a successful training)
- Participants who were unable to successfully complete the insertion/removal training will exit the study now.

Visit 2: 1-week follow-up and study exit, day 6-10 days after Visit 1 or Visit 1B-R

Participant to attend visit after 2 hours or more of contralateral study lens wear.

- Collect unused study CLs;
- Changes in medical history/medications;
- LogMAR HIHC VA for OD, OS and OU with study lenses
- Compliance (# of CL wear days; total and comfortable hours of wear);
- Subjective ratings for wear experience with both CLs (0-100 scale, where 100 means better performance; integer steps, ratings for each eye individually for a typical day in the last week);
 - Comfort (at insertion and just before removal)
 - Handling (insertion & removal)
 - General handling questions
- Preference ratings between study lenses:
 - Comfort
 - Handling for insertion
 - Handling for removal
 - Overall
 - Willingness to purchase
- Lens fit assessment (Overall Lens Fit acceptance (0-4, 0.5 steps), Lens Wettability (0-4, 0.25 steps), Lens Tightness (0-100, 1 step), Lens Centration (0-3, 1 step)
- Lens removal

Study Exit:

- Biomicroscopy examination (Efron scale) SAFETY
 - External adnexa anomalies
 - o Cornea & anterior eye assessment for scars, infiltrates

- Bulbar & limbal redness
- Corneal & conjunctival staining with fluorescein dye
- Palpebral conjunctival hyperemia & roughness
- Exit logMAR HIHC VA for OD, OS and OU (habitual spectacles) SAFETY;
- Study exit forms & remuneration.

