11 STATISTICAL ANALYSIS AND DATA MANAGEMENT

11.1 STATISTICAL ANALYSIS

All data will be analyzed by CORE at the University of Waterloo. Descriptive statistics will be provided on information regarding baseline variables (e.g. age, gender). Differences between lenses and differences over time will be compared using either Paired t-tests or Wilcoxon matched pairs, or using ANOVA, as applicable; statistical significance will be set at 5%. The appropriate tests will be selected based on tests of normality - non-parametric tests will be used for data not showing a normal distribution. For assessments conducted for each eye separately, the right eye will be used for analysis.

Subjective ratings for lens handling with Precision1 and 1-Day ACUVUE Moist as determined at study Visit 1 (or Visit 1B-R) (after successfully completing the lens handling training) will also be compared using superiority testing, with a margin of 5 points on a 100-point scale.

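### The plan leaves open whether a valid primary handling rating can be dropped because of what happens at or before Visit 2; the primary analysis set should be every participant who rated both lenses after training

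*Combined protocol and SAP*

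**What the plan says.** **Timing of the primary endpoint.** Section 2 defines it as "Subjective ratings of lens handling for insertion and removal as determined during the handling training component during Visit 1 (and Visit 1B-R"). Section 5.4.2 collects the ratings only from participants who have passed training, and lists them ahead of wear instructions and lens dispensing.

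**Who is analysed.** Four places bear on this:

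- Section 6: "Visit windows will be reviewed when determining the analysis cohort". It speaks of one cohort and does not separate endpoints.
- Section 5.2.1: the number required "is 32 to complete the study and be eligible for data analysis". Up to 60 may be randomized and dispensed lenses, to allow for drop-out that the section associates with adaptation and handling. Section 5.2.2 repeats the target: "with a target of number of 32 participants completing the study".
- Section 9: on discontinuing, participants are offered the choice of having their data withdrawn from later analysis.
- Section 11.1: the superiority comparison uses ratings "as determined at study Visit 1 (or Visit 1B-R) (after successfully completing the lens handling training"). Passing training is the only condition attached. No analysis population or missing-data rule is given.

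**Visit windows.** The only numeric one is in section 5.4.2 (matching the wear period in 5.1.1): "Visit 2: 1-week follow-up and study exit, day 6-10 days after Visit 1 or Visit 1B-R".

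**The concern.** Visit 2 attendance, its timing and study completion all come after the primary outcome has been recorded. None of them affects whether a post-training rating is valid. Yet sections 6 and 5.2.1, read together, allow a cohort for the primary comparison that is restricted by exactly those events.

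The main risk is selection. The plan itself expects some participants to leave because of adaptation or handling problems, and handling is the primary outcome. If the between-lens difference among those who leave differs from that among those who stay, a completers-only estimate no longer describes everyone who was trained and gave ratings. The comparison is judged against a 5-point margin, so a shift of one or two points can matter. A lesser cost is the loss of precision from ratings already collected.

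**Working it through.** **1. Reproduce the planned sample size.** Inputs from section 5.2.1: two-sided paired t-test, α = 0.05, power 0.90, effect size 0.60, difference 5 points. The implied SD of the paired differences is 5 / 0.60 = 8.33.

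Exact power uses the noncentral t with n − 1 degrees of freedom and noncentrality 0.60 × √n:

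- n = 31: 0.898
- n = 32: 0.908

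The smallest n reaching 0.90 is 32, as stated. The figure is right; the open question is whom it counts.

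**2. Set the passages side by side.**

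| Place | Bearing on a participant with both primary ratings but a late or missed Visit 2 |
|---|---|
| Section 6 | The window is reviewed when the single cohort is set; exclusion is possible |
| Section 5.2.1 | Completion and eligibility for analysis are stated together; suggests exclusion |
| Section 9 | Withdrawal of data is the participant's option; suggests retention otherwise |
| Section 11.1 | The only condition is passing training; suggests retention |

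The over-enrolment matters here. Someone who drops out after dispensing has already given the primary ratings. For the primary test, an allowance for that drop-out makes sense only if such people are not counted.

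**3. Upper bound on ratings affected.** 60 − 32 = 28, and 28 / 60 = 46.7%. This needs all 60 to pass training and give ratings. Lens randomization takes place in Visit 1 Part A, before training, and 60 is also the recruitment cap in section 5.2.2. Screening, fitting or training failures would lower the count.

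**4. Precision.** The 95% CI half-width is t(0.975, n − 1) × 8.33 / √n. Power is for the test in section 5.2.1.

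| n analysed | Half-width (points) | Power |
|---|---|---|
| 32 | 3.00 | 0.908 |
| 40 | 2.67 | 0.959 |
| 60 | 2.15 | 0.995 |

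The 40 corresponds to an assumed 20% loss after rating: 32 / 0.80 = 40 rated to give 32 completers.

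**5. Illustration of selection (assumed values).** Let p be the share lost after rating and m their mean lens difference, and suppose the mean in all rated participants is 5. Then the completer mean = (5 − p × m) / (1 − p).

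| p | m = −5 | m = 0 | m = 10 |
|---|---|---|---|
| 10% | 6.11 | 5.56 | 4.44 |
| 20% | 7.50 | 6.25 | 3.75 |
| 30% | 9.29 | 7.14 | 2.86 |

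If m = 5 there is no bias at any p. Neither p nor m comes from the documents. The table shows only that the shift can go either way and can be material against a 5-point margin.

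**The case against.** A reader might infer that the plan requires a participant to be removed from the primary analysis for attending on day 11 or for stopping wear. The documents do not say so. Section 6 says windows are reviewed, not that out-of-window participants are excluded, and that is an ordinary check for the endpoints measured at Visit 2. Section 5.2.1 sets a recruitment target rather than an analysis set, and 32 completers also serve the Visit 2 endpoints. The opt-out in section 9 makes sense only if discontinued participants' data otherwise remain available, and section 11.1 asks only that training was passed. All of this stands, and it limits the point to exclusion that is permitted rather than mandated.

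Three further limits also stand:

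- Each participant rates both lenses, so general difficulty with handling affects both ratings. Bias needs a different between-lens difference in those who leave.
- Planned power is met at 32. The higher power at 40 or 60 was never promised, so lost precision is not a design failure.
- Investigators and participants stay masked until database lock (section 5.1.2). That limits opportunistic exclusion if the cohort is fixed before unmasking, but the documents do not say when it is fixed, and masking does not prevent selection through drop-out.

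The objection does not remove the conflict. Sections 5.2.1 and 6 lean one way, sections 9 and 11.1 the other, and no sentence settles which participants enter the primary comparison.

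**Conclusion.** The point holds as a conflict over the primary analysis set that should be resolved before unmasking. The text allows valid paired primary ratings to be left out because of later events that the plan itself partly links to handling, and nothing commits to keeping them.

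The sample size is correct, and 32 analysed participants keep power at 0.908 under the assumed SD of 8.33. A reader might take 47% as an expected loss. It is only the arithmetic ceiling, since no drop-out rate is given and some of the 60 may have no rating to lose. Nor do the documents support a claim that the result would be biased towards either lens. The size and direction of any bias are unknown, and the values in the selection table are assumptions.

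**What to change.** In section 11.1, state that the primary analysis includes every participant with post-training ratings for both lenses at Visit 1 or Visit 1B-R, regardless of Visit 2 timing, attendance or study completion, except where the participant has withdrawn their data under section 9.

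In section 6, limit the review of the 6-10 day window to the Visit 2 endpoints. In section 5.2.1, separate the two ideas: at least 32 participants with paired post-training ratings for the primary test, and a target of 32 completers for the Visit 2 endpoints. Report the primary comparison in completers as a sensitivity analysis.

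The cost is wording only: no new data, visits or participants.

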7 POTENTIAL RISKS AND BENEFITS TO HUMAN PARTICIPANTS

This is a minimal risk study because of the use of marketed products and standard optometric assessments.

Contact lenses in this study will be worn on a daily wear (and daily disposable) basis. Adverse events and/ or complications in daily wear of soft contact lenses can occur (e.g. inflammation and infection). Complications that may occur during the wearing of contact lenses include discomfort,

dryness, aching or itching eyes, excessive tearing, discharge, hyperemia and variable or blurred vision. More serious risks may include photophobia, iritis, corneal edema or eye infection. Although contact lens-related infections are very infrequent, the possibility does exist. The incidence of infection due to daily-wear soft lenses is 0.035%. Almost always an infection will occur only in one eye. Thirty five million Americans who currently wear contact lenses assume this risk.

When contact lenses are worn on a daily wear basis there is a small risk of an adverse event compared to not wearing contact lenses. When contact lenses are worn on an extended wear basis, there is a significantly increased risk of an adverse reaction compared with wearing contact lenses on a daily wear basis.

A dye (fluorescein) normally used for eye exams is being used in this study. Although rare, it is possible that participants may have an allergic reaction to the dye. This could cause discomfort to their eye.

Participants are advised to inform the investigator of any sensitivities to any ophthalmic drops or study products.

Additionally, it is possible that participants may experience temporary discomfort associated with the study procedures /products including: burning and stinging, blurred vision, sandiness or grittiness, light sensitivity, dryness, itching, crusty eyes and foreign body sensation.

Participants will have the opportunity to try two different types of soft contact lenses at no cost to them. They will be trained on lens handling for lens insertion and removal and will be provided with instructions to safely wear daily disposable contact lenses.

Participation in this study may contribute to scientific research information that may be used in the development of new contact lens products. Information from this study may help researchers and the funding company to better understand if the use of specific daily disposable lens types in neophyte lens wearers.

8 ADVERSE EVENTS

See CORE SOP012_v02 for a description of all adverse events, including management and reporting.

Any observations taking place prior to determining that a subject meets all inclusion/ exclusion criteria for the study and which are not related to the performed study procedures are not considered an AE. An AE can be any unfavourable and unintended sign, symptom, or disease temporarily associated with a study procedure, whether there is a causal relationship or not.

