5.2.3 INCLUSION AND EXCLUSION CRITERIA

A person is eligible for inclusion in the study if he/she:

- 1. Is between 18 and 40 years of age inclusively and has full legal capacity to volunteer;
- 2. Has read and signed an information consent letter;
- 3. Is willing and able to follow instructions and maintain the appointment schedule;
- 4. Is a neophyte who has no history of any previous contact lens handling experience;
- 5. Has a refraction cyl ≤1.00DC in either eye (after vertexing to corneal plane);
- 6. Has visual acuity ≤0.20 logMAR each eye with study lenses;
- 7. Demonstrates acceptable fit with study lenses;
- 8. Demonstrates the ability to successfully insert and remove the study lenses 3 times for each eye (contralateral CL handling, so that each lens type inserted and removed 3x on same eye);
- 9. Is willing to wear study CLs at least 5 days per week and 6 hours per day throughout the study

A person will be excluded from the study if he/she:

1. Is participating in any concurrent clinical or research study;

- 2. Has any known active* ocular disease and/or infection;
- 3. Has a systemic condition that in the opinion of the investigator may affect a study outcome variable;
- 4. Is using any systemic or topical medications that in the opinion of the investigator may affect a study outcome variable;
- 5. Has known sensitivity to the diagnostic pharmaceuticals to be used in the study;
- 6. Is pregnant, lactating or planning a pregnancy at the time of enrolment (by self-report);
- 7. Is aphakic;
- 8. Has undergone refractive error surgery;
- 9. Has taken part in another clinical research study within the last 14 days;
- 10. Any ocular and/or systemic conditions or concomitant medication to contraindicate contact lens wear or be expected to interfere with the primary outcome variables.
- * For the purposes of this study, active ocular disease is defined as infection or inflammation which requires therapeutic treatment. Mild (i.e. not considered clinically relevant) lid abnormalities (blepharitis, meibomian gland dysfunction, papillae), corneal and conjunctival staining and dry eye are not considered active ocular disease. Neovascularization and corneal scars are the result of previous hypoxia, infection or inflammation and are therefore not active.

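### Until handling training is passed, Section 8 counts an event in a lens-exposed participant as an adverse event only if it is judged related to study procedures

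*Combined protocol and SAP*

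**What the plan says.** Section 8 (Adverse Events) does three things. It refers out for detail: "See CORE SOP012_v02 for a description of all adverse events, including management and reporting". It then sets an exclusion with two conditions, one of time and one of causality: "Any observations taking place prior to determining that a subject meets all inclusion/ exclusion criteria for the study and which are not related to" the procedures performed do not count as AEs. Finally it gives a general definition, under which an AE can be an unfavourable sign, symptom or disease "temporarily associated with a study procedure, whether there is a causal relationship or not".

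Section 5.2.3 lists the criteria to which the time condition refers. Three of them need the study lenses:

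- Criterion 6: "Has visual acuity ≤0.20 logMAR each eye with study lenses".
- Criterion 7: "Demonstrates acceptable fit with study lenses".
- Criterion 8: "Demonstrates the ability to successfully insert and remove the study lenses 3 times for each eye".

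Section 5.4.2 fixes the order. Lenses are randomized to eyes and placed by the investigator in Visit 1 Part A, and the participant practises in Part B. Those who do not succeed are offered Visit 1B-R. "Only those participants able to insert/remove lenses at Visit 1 (or Visit 1B-R) will continue in the study"; the others exit.

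**The concern.** An exclusion for observations made before eligibility normally keeps pre-existing findings out of the AE listing. In this trial the eligibility point comes after exposure, so the same sentence also covers a period in which first-time wearers have had both lenses on the eye and have practised inserting and removing them.

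What is at stake is the completeness of the safety record in that period. Section 7 names discomfort, itching and hyperemia among the complications of lens wear. Signs of this kind can readily be put down to an allergy or a cold, both of which Section 5.2.4 gives as examples of transient conditions affecting the eye. If they are so attributed before training is passed, they are not AEs. They then fall outside the AE review in Section 6 and the AE details monitored under Section 13. People who struggle with handling stay longest under this rule, and a study of handling in neophytes should expect some of them.

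**Working it through.** No figure in the plan bears on this point, so the check sets the sections side by side.

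**Step 1. When does each stage fall relative to lens exposure and eligibility?** (Sections 5.4.2 and 5.2.3)

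| Stage | Study lens already on the eye? | All criteria determined? |
|---|---|---|
| Part A: consent, history, biomicroscopy, refraction, randomization | No | No |
| Part A: fitting by the investigator; criteria 6 and 7 judged | Yes | No |
| End of Part A: check that permits Part B | Yes | No; criterion 8 is still untested |
| Part B: training in progress | Yes | No |
| Part B: training passed | Yes | Yes |
| Interval to Visit 1B-R, for those who failed | Yes | No |
| Visit 1B-R: training passed | Yes | Yes |
| Visit 1B-R: training failed, exit | Yes | Never |

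**Step 2. What does Section 8 make of an event in each period?**

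| Period | Judged related to procedures | Judged not related |
|---|---|---|
| Before first lens | AE | Not an AE |
| First lens until training passed | AE | Not an AE under the exclusion, although the general definition would admit it |
| After training passed | AE | AE if associated in time with a study procedure |

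The disputed cell is the middle row, right-hand column. An example is a red eye that arises between Visit 1 and Visit 1B-R and is attributed to allergy. The exclusion removes it. The general definition, which applies "whether there is a causal relationship or not", would keep it.

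**Step 3. How long is the window?** (scheduled times from Table 2)

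- Pass at Visit 1: from first insertion in Part A to the end of training, so less than 1 h + 1 h = 2 h of scheduled time.
- Pass at Visit 1B-R: less than 1 h + 1 h + 1 h = 3 h of scheduled time, plus an interval between visits for which no limit is stated.
- Never pass: all participation from first lens placement onward.

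Section 5.2.4 allows up to three screenings, including when procedures could not be finished in the scheduled time, so the window may be longer still.

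**Step 4. What information supports the causality judgement in the window?** Table 3 and Section 5.5.1 have participants asked at Visit 1B-R about changes in health and medication, so events from the interval will be elicited and must then be classified. Table 3 marks biomicroscopy at Visits 1 and 2 but not at Visit 1B-R, and the Visit 1 list places it before fitting. Section 5.5.7 says corneal observations are documented at every visit, which does not match Table 3 for Visit 1B-R. As scheduled in Table 3 and Section 5.4.2, someone who fails training and exits has no slit-lamp examination after lens exposure.

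**The case against.** The strongest reply is that the two sentences of Section 8 do not conflict. The first is a specific exception and the second a general definition, which is ordinary drafting. That reading is available, so it would be too strong to say the section gives opposite answers. But the exception, so read, is exactly what puts a causality filter on lens-exposed participants.

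A reader might infer that no AE is recorded until eligibility is complete. The text does not say so. The exclusion needs both conditions, and Table 3 lists fitting and training as procedures. An abrasion judged to result from training is an AE from the first insertion, including in someone who never passes.

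A reader might infer that only training failures are filtered. Everyone is, until they pass. The difference is one of duration.

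A reader might infer a bias between lenses. Each participant wears both lenses, one per eye. Sections 5.1.2 and 5.1.3 mask investigators and participants, AEs are not among the endpoints in Section 2, and Section 11.1 plans no AE comparison. The issue is missed events and not a tilt towards one product.

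A reader might take 60 − 32 = 28 as the size of the affected group. Section 5.2.1 describes the 60 as randomized and dispensed, and lenses are dispensed only after successful training, so on that wording the 28 would already have passed. Section 5.2.2 also uses 60 as a recruitment cap. The figure does not measure training failures and should not be used.

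Some information is kept elsewhere: health changes at Visit 1B-R, unscheduled-visit data (Section 5.4.3), and reasons for discontinuation in the final report (Section 9). This reduces the loss, but such entries do not go through AE review.

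The cited SOP is not among the documents and may set a different start point. If so, the sentence in Section 8 conflicts with it and still needs correcting.

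Lastly, wider capture might turn expected brief discomfort into AEs. Such symptoms, where caused by the procedures, are already AEs under the current text, so the change should add little on that account.

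**Conclusion.** The concern holds in a limited form. Between first study-lens placement and passing training, Section 8 makes AE status depend on a judgement of relatedness. For participants who never pass, that condition is never lifted. AE counts can therefore be understated. Whether they would be, and by how much, cannot be determined: the documents give no number of training failures, no event rate in the window and no rate of misattribution.

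The conclusion rests on three assumptions: that Section 8 is applied as written, that the SOP does not override it, and that the association in the general definition means association in time.

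This is a safety-reporting matter in a study that the protocol describes as minimal risk. It does not affect the primary handling comparison or the target of 32 completers. It is worth correcting because the rule is stated, does not fit the visit order, and is cheap to change.

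**What to change.** Reconcile Section 8 with the visit order in Section 5.4.2. Suggested wording: *Observations made before the first study lens is placed on the eye at Visit 1 Part A, and not related to study procedures, are baseline findings and not AEs. From first lens placement, the AE definition in this section applies whatever the participant's eligibility status and whatever the judged relationship.* Add that AEs will be reported for all participants who had a study lens on the eye, including those who fail training, and confirm that the SOP agrees.

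The cost is one replaced sentence, a reporting line, a CRF start point at first lens placement, and possibly a higher AE count. Eligibility, sample size and the primary analysis do not change.
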